#### 8. OUTPUT PRESENTATIONS

Appendix 1 shows conventions for presentation of data in outputs.

The mock up TFLs shell provided with this SAP describe the presentations for this study and therefore the format and content of the summary tables, figures, and listings to be provided by IQVIA Biostatistics.

Summary statistics for continuous variables will include the mean, standard deviation, median, interquartile range, and range (minimum/maximum). Categorical variables will be presented as frequency counts and percentages, and time-to-event variables will be summarized with number

Document: \(\)\ieedc-vnac01\\Biosdata\\Genexine\\GX-188E\\GYA02599\\Biostatistics\\Documentation\\SAP\)

Author: [name] Version Number: 1.1

Version Date: 05Sep2022

Template No: CS\_TP\_BS016 Revision 6 Reference: CS\_WI\_BS005

Effective Date: 02Dec2019

Analysis Plan

Genexine

PROTOCOL GX-188E-005

Page 21 of 48

of non-missing observations, median time, and survival probability using Kaplan-Meier method if applicable. Kaplan Meier plot will also be provided.

The data will be tabulated and analyzed with respect to patient enrollment and disposition, demographic and baseline characteristics, prior and concomitant medications, efficacy, and safety results. The efficacy analysis will be conducted on the Efficacy Evaluable Population, and the safety analysis will be performed on the Safety Population.

Data listings will be created to support each table and to present all data collected.

#### 9. DISPOSITION AND WITHDRAWALS

All patients who provide informed consent will be accounted for in this study. Patient disposition and withdrawals will be presented for all patients enrolled population. Patient disposition and withdrawals include information about patients enrolled, patients who received study medication, patients who completed/withdrew from study medication/study, reason for study medication withdrawal and study early termination. The breakdown of patients into the analysis sets will be presented.

A listing of inclusion/exclusion criteria deviations and reason for screen failure will be provided for screen failure patients.

Additionally, IQVIA clinical trial management system (CTMS) protocol deviation (PD) will be used. Any protocol deviations identified during the course of the study will be listed and the number and percentage of patients in each type of protocol deviations will be summarized for the SAF.

Follow-up time (months) is the time between a specified event (death, end of the study, follow-up date or completion/ last contact date, whichever occurred later) and the date of first dose.

• Follow-up time (months) = (the date of event-the date of first dose +1)/30.4375

Follow-up time will be summarized for safety population.

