# 16.13 Long-Term Follow-Up

Patients will enter into the long-term follow-up phase of the study after the EOS visit to obtain survival data. Survival data may be obtained either by clinic visit or by remote communication (e.g., telephone call or email) or hospital medical records. Sites must follow up with patients approximately every 4 months for up to 1 year to obtain the following data:

- Survival status: Is the patient still living? (Yes or No)
  - o If "No", what was the approximate date of death?
- Has the patient received any subsequent active anti-cancer treatment (this does not include palliative measures)? (Yes or No)
  - o If "Yes", what treatments has the patient received?

Family members, primary care giver, public records, or primary treating oncologist/oncologist's office may confirm a patient's death.

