#### 7.3. MISSING DATA

Generally, missing data will not be imputed.

For death date, if year and month of death date are known but the day of date is unknown, day will be imputed as 1. For example, if a patient is reported to die on Dec 2016, the death date will be imputed as 01Dec 2016.

Imputed dates will NOT be presented in the listings.

Partial dates of adverse events and prior/concomitant medication will be handled as described in Appendix 2.

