#### OS

Overall survival is defined as the time from treatment initiation until death from any cause. Median OS time (months) is the timepoint at which the probability of survival equals 50% in the efficacy evaluable population. Patients developing no event will be censored on the last known survival date. Patients providing no follow-up information will be censored on the day of first dosing. Kaplan-Meier method will be used to estimate median OS and the corresponding 95% CI. Kaplan-Meier curves will be constructed to provide a visual presentation of the OS rate change with time.

6-month OS rate is the proportion of efficacy evaluable patients who are alive 6 months after treatment initiation. The OS rate and 95% CI at 6 months will also be summarized.

OS will be displayed for Part A, Part B and Part C.

Waterfall, Spider, Swim-lane and forest Plots

A waterfall plot will be prepared to visually present the best percentage change from baseline in sum of diameters in target lesions for each patient grouped by PD-L1 status, HPV type, and histologic type.

A Spider Plot will be used to visualize changes in sum of diameters in target lesions with best overall response by BICR according to RECIST 1.1. With a Spider Plot, post-baseline measurements are compared to the baseline. Thus, the data plotted is the percent change from baseline over the period of patient evaluation. Each leg of the "spider" represents a unique patient.

Swim-lane Plot for Tumor Response will be presented to show tumor assessment by at each

Document: \\ieedc-vnac01\Biosdata\Genexine\GX-188E\GYA02599\Biostatistics\Documentation\SAP

Author: [name] Version Number: 1.1

Version Date: 05Sep2022

Template No: CS\_TP\_BS016 Revision 6 Reference: CS\_WI\_BS005

PROTOCOL GX-188E-005

Analysis Plan Page 34 of 48

visit. Specifically, the Swim-lane plot will show total time to tumor response, whether the response was complete or partial, when the response started/ended and censoring information of the patient grouped by PD-L1 status, HPV type, and Histologic type.

These plots will be displayed only for Part C.

In Part C, a forest plot will be used to display BICR Assessed BORR according to RECIST v1.1 across subgroups.

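### The SAP ends follow-up time at the latest of several dates without stopping at death, so a patient whose recorded contact date falls after death would be credited with follow-up after dying

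*SAP*

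**What the plan says.** SAP section 9 (Disposition and Withdrawals) defines follow-up time as running from first dose to one of "death, end of the study, follow-up date or completion/ last contact date, whichever occurred later". The formula is "Follow-up time (months) = (the date of event-the date of first dose +1)/30.4375", and "Follow-up time will be summarized for safety population". The section makes no exception for patients who died. The SAP does not say, for this variable, that last contact means the last date the patient was known to be alive.

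Protocol section 16.13 (Long-Term Follow-Up) describes how survival data arise after the End of Study visit: "Sites must follow up with patients approximately every 4 months for up to 1 year to obtain the following data". Sites ask whether the patient is living and, if not, for an approximate death date. The source need not be the patient: "Family members, primary care giver, public records, or primary treating oncologist/oncologist's office may confirm a patient's death".

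SAP section 15.2 (OS) treats the same patients differently. Survival time stops at death from any cause, and "Patients developing no event will be censored on the last known survival date".

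**The concern.** A death between two scheduled survival contacts is likely to be learned at a contact dated after it. If that date is entered as the follow-up or last contact date, it is the latest in the list and the rule selects it. The patient's follow-up time then exceeds her survival time, although she was not under observation for any event in the difference. The same patient would have one end date in the follow-up summary and an earlier one in the OS analysis.

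At stake is the accuracy of a descriptive figure that accompanies the safety results. The added time arises only in patients who died, so its size depends on how many deaths occur between contacts and how late they are reported.

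**Working it through.** The documents state no follow-up figure, so there is none to reproduce. The divisor is right: 365.25 / 12 = 30.4375 days per month.

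**Direction.** Let D be the death date and C the latest other date in the list. The SAP rule uses max(D, C). This is never earlier than D, so the rule can overstate follow-up for a patient who died but cannot understate it relative to the recorded death date.

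**One hypothetical patient (dates assumed).** First dose 04Jan2021, death 10Sep2021.

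- Ending at death: (249 + 1) / 30.4375 = 8.21 months.
- SAP rule, contact on 10Nov2021: (310 + 1) / 30.4375 = 10.22 months, an excess of 2.00.
- SAP rule, contact on 10Jan2022: (371 + 1) / 30.4375 = 12.22 months, an excess of 4.01.

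**Partial death dates.** SAP section 7.3 adds that "if year and month of death date are known but the day of date is unknown, day will be imputed as 1". If only September 2021 is known, the death date becomes 01Sep2021. With contact on 10Jan2022, the excess over the imputed death date is (372 − 241) / 30.4375 = 4.30 months. Part of that gap comes from the imputation rather than from the follow-up rule.

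**Range per affected patient.** With contacts about 4 months apart (Protocol section 16.13), the lag from death to the next contact is 0 to about 4 months. If deaths fall evenly over the interval and are learned only at the next contact (both assumptions), the average lag is (0 + 4) / 2 = 2 months.

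**Effect on the mean.** Increase in mean follow-up = share of patients affected × mean lag. The documents give neither input, so the table shows a range.

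| Share affected (assumed) | Mean lag 1 month | Mean lag 2 months | Mean lag 4 months |
|---|---|---|---|
| 10% | 0.1 | 0.2 | 0.4 |
| 30% | 0.3 | 0.6 | 1.2 |
| 50% | 0.5 | 1.0 | 2.0 |

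The 4-month column is an extreme, in which every affected death is learned a full interval late. The effect on the median also depends on the shape of the survival and treatment-duration distributions, which the documents do not give.

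**What else uses this variable.** ORR24 (SAP 15.1) and DOR, PFS and OS (SAP 15.2) each have their own definitions, with event and censoring dates for the time-to-event endpoints. None refers to the follow-up time of section 9.

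**The case against.** The strongest objection is that the excess depends on a case report form that the documents do not show. SAP sections 5.4 and 16.2 refer to a separate death details page. Nothing shows whether a follow-up or contact date is entered after a death, or whether it holds the date of the call or the last date the patient was known alive. Public or hospital records can also supply a death date without producing a later contact date. This stands: the documents support saying that follow-up would be overstated for any patient with a later recorded date, not that the reported figure will be overstated.

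A second objection is grammatical. The closing words of the rule could attach only to the follow-up and last contact dates, leaving death as an end point of its own. That reading is possible. The SAP would then not say which listed event applies to a given patient, and two programmers could derive different values, so the sentence needs correcting either way.

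A third is that a fixed amount of inflation cannot be claimed. This also stands. Any such figure needs assumed survival, time on treatment and reporting lag. The excess shrinks if deaths are learned promptly. It may also shrink if the data are cut early, and SAP section 4.3 ties the final analysis to 24-week tumor assessments with some patients possibly still on treatment.

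A reader might also infer that OS, PFS or DOR is distorted, or that the plan judges their maturity by this figure. The documents do not support either. Those endpoints have separate rules and are analysed in the efficacy evaluable population, whereas follow-up time is a disposition summary for the safety population. No planned test, confidence interval or decision uses it.

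**Conclusion.** The rule is wrong as written. Taking the latest date with no stop at death allows time after death to count as follow-up, and it conflicts with the SAP's own OS rule for the same patient. The retrospective survival contacts in the protocol make a contact date after death a plausible data pattern.

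The consequence is small and confined to one descriptive summary; no endpoint result changes. The per-patient range rests on the 4-monthly contact schedule, and the 2-month average on evenly spread deaths learned only at the next contact. Any shift in the mean or median is illustrative. Confidence is medium: the wording is clear enough to need correction, but whether it bites depends on what date is recorded after a death.

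**What to change.** In SAP section 9, replace the end-date rule with: for patients who died, follow-up time ends at the date of death; for all other patients, it ends at the last date known alive on or before the data cut-off.

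This agrees in principle with the OS event and censoring dates in SAP section 15.2. The match is not exact, because the OS text states no cap at the cut-off and has a separate first-dose rule for patients with no follow-up information.

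The cost is one sentence in the SAP and the matching derivation. No new data are needed, and reported follow-up can only stay the same or become shorter for patients who died. If the sponsor also wants a median follow-up to support the maturity of OS or DOR, that is a separate quantity. Its method should be stated, for example reverse Kaplan-Meier, because follow-up that ends at death mixes observation time with survival.

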#### 10. Demographic and other Baseline Characteristics

Demographic data and other baseline characteristics will be presented for the DLT evaluable population, safety population and efficacy evaluable population.

Descriptive statistics will be used for summarizing the patients' characteristics. No statistical testing will be carried out for demographic or other baseline characteristics.

Document: \\ieedc-vnac01\Biosdata\Genexine\GX-188E\GYA02599\Biostatistics\Documentation\SAP

Author: [name] Version Number: 1.1

Version Date: 05Sep2022

Template No: CS\_TP\_BS016 Revision 6 Reference: CS\_WI\_BS005

Effective Date: 02Dec2019

PROTOCOL GX-188E-005

Analysis Plan Page 22 of 48

The following demographic and other baseline characteristics will be summarized for this study. Individual data will also be listed.

- Age (years) calculated relative to date of consent
- Childbearing potential
- Race
- Ethnicity
- Weight (kg)
- BMI (kg/m²)
- ECOG Performance Status
- Moore's criteria for determining prognosis in cervical cancer
- PD-L1 test result

#### 10.1. DERIVATIONS

- BMI (kg/ m²) = weight (kg)/ height (m)²
- Age (years) = Year of informed consent (IC) Year of birth, if month of IC is later than
  month of birth, or if month of IC is equal to month of birth but day of informed consent is
  later than or equal to day of birth;

Age (years) = Year of informed consent – Year of birth – 1, otherwise.

In this case, if one patient is more than 45 years old but less than 46 years old, then this patient will be presented as age 45.

#### 11. MEDICAL HISTORY

Medical History information will be presented for the safety population.

General Medical History will be coded using Medical Dictionary for Regulatory Activities (MedDRA), Version 21.1 or higher. Data captured on the "Medical History – General" form of the Case Report Form (CRF) will be presented in frequency table by System Organ Class (SOC) and Preferred Term (PT) in descending order of total frequency. For SOCs or PTs with the same total frequency, categories will be sorted alphabetically.

 $Document: \underline{\label{locality} Nieedc-vnac01\\Biosdata\\Genexine\\GX-188E\\GYA02599\\Biostatistics\\Documentation\\SAParticles \\Documentation\\SAParticles \\Documentation\\SAParticles \\Documentation\\SAParticles \\Documentation\\SAParticles \\Documentation\\SAParticles \\Documentation\\SAParticles \\Documentation\\SAParticles \\SAParticles \\SAParti$ 

Author: [name] Version Number: 1.1

Version Date: 05Sep2022

Template No: CS\_TP\_BS016 Revision 6 Reference: CS\_WI\_BS005

Effective Date: 02Dec2019

Analysis Plan Page 23 of 48

Medical History data captured on the "Medical History – Cancer and HPV" will be presented. The following information will be summarized:

- Medical History Term by SOC and PT (HPV and Advanced inoperable or metastatic cervical cancer)
- Histologic Type at diagnosis
- Stage of disease at diagnosis
- Stage of disease at enrolment
- HPV Variant (HPV 16+/ HPV 18+/ Other)
- Type of anti-cancer therapy (Prior oncologic drugs and biologics / Prior oncologic surgery and procedures / Prior oncologic radiation)
- Target Lesion(s) at time of screening (Uterus, Lymph node, Liver, Lung, Spleen, Bone, Adrenal Gland, Tubes, Ovaries, Vagina, Bladder, Urethra, Rectum, Others)
- Non-Target Lesion(s) at time of screening (Uterus, Lymph node, Liver, Lung, Spleen, Bone, Adrenal Gland, Tubes, Ovaries, Vagina, Bladder, Urethra, Rectum, Others)

Medical history data will be listed.

#### 12. MEDICATIONS AND PROCEDURES

## 12.1. PRIOR AND CONCOMITANT MEDICATIONS AND NON-DRUG TREATMENT

All concomitant medications received by the patient within 28 days prior to the first dose through the end of the patient's study participation should be recorded on the "Prior and Concomitant Medications" page of CRF. Prior medications are those medications that were stopped prior to first study treatment. Concomitant medications are medications taken at least once after first study treatment. Medications stopped on the same day as first study treatment will be considered as prior medication only.

Prior and concomitant medications will be coded using the World Health Organization Drug Dictionary. The PT will be used for tabulation. The summary tables will show the number and percentage of patients by PT, for each part and overall. Pre and concomitant medications will be summarized separately. The descriptive summaries for pre and concomitant medications will be

Document: \\ieedc-vnac01\Biosdata\Genexine\GX-188E\GYA02599\Biostatistics\Documentation\SAP

Author: [name] Version Number: 1.1

Version Date: 05Sep2022

Template No: CS\_TP\_BS016 Revision 6 Reference: CS\_WI\_BS005

Effective Date: 02Dec2019

PROTOCOL GX-188E-005

Analysis Plan Page 24 of 48

presented for the safety population. Missing or partial dates for medications will be handled according to Appendix 2 of this analysis plan. In the case where it is not possible to define a medication as prior or concomitant, the medication will be classified by the worst case; i.e. concomitant. For the summaries of concomitant medications, patients who take the same medication (in terms of the PT), more than once will only be counted once for that medication. The detailed information of prior and concomitant medication use including medication name, indication, dose, start date, end date, ongoing or not, frequency and route of administration, etc. will be listed.

Non-Drug treatment will be collected on the "Prior and Concomitant Non-Drug Treatment" form of CRF including procedure name, indication, start date, end date and ongoing or not. Non-Drug treatment name will be coded using MedDRA Version 21.1 or higher version. Non-Drug treatment information will be summarized by SOC and PT. Non-Drug treatment will be listed for safety population.

#### 12.2. PRIOR ANTI-CANCER THERAPIES

Information collected on the "Prior Oncologic Drugs and Biologics", "Prior Oncologic Surgery and Procedure", and "Prior Oncologic Radiation" pages of CRF will be summarized descriptively.

#### 12.3. Subsequent Anti-Cancer Therapies

Subsequent new anti-cancer therapy after the end of the study will be listed.

#### 13. STUDY MEDICATION EXPOSURE

Exposure data will be presented for the safety population.

The date of first study medication administration will be taken from the CRF "Exposure – GX-188E" and "Exposure – Pembrolizumab" form. The date of last study medication will be taken from the "Date of last administration" on "End of Treatment" page of CRF for GX-188E and Pembrolizumab.

The variables relevant to the extent of exposure listed as below will be summarized for safety population. Individual exposure data recorded in "Exposure – GX-188E" and "Exposure – Pembrolizumab" as well as the derived variables will also be listed.

#### Duration of exposure of GX-188E

 $Document: \underline{\label{locality} Nieedc-vnac01\\Biosdata\\Genexine\\GX-188E\\GYA02599\\Biostatistics\\Documentation\\SAParticles \\Documentation\\SAParticles \\Documentation\\SAParticles \\Documentation\\SAParticles \\Documentation\\SAParticles \\Documentation\\SAParticles \\Documentation\\SAParticles \\Documentation\\SAParticles \\SAParticles \\SAParti$ 

Author: [name] Version Number: 1.1

Version Date: 05Sep2022

Template No: CS\_TP\_BS016 Revision 6 Reference: CS\_WI\_BS005

Effective Date: 02Dec2019

PROTOCOL GX-188E-005

Analysis Plan Page 25 of 48

- Number of Doses of GX-188E
- Percentage of Patients with GX-188E interruption
- Duration of exposure of Pembrolizumab
- Number of Doses of Pembrolizumab
- Percentage of Patients with Pembrolizumab interruption

The information of the overdose, abuse and accidental exposure of GX-188E and Pembrolizumab will be collected in "Overdose, Abuse, Accidental Exposure – GX-188E" and "Overdose, Abuse, Accidental Exposure – Pembrolizumab" form in CRF. The overdose, abuse and accidental exposure data will be listed for safety population.

#### 13.1. DERIVATIONS

- Duration of exposure to GX-188E (weeks)= (Last dose date of GX-188E First dose date of GX-188E +1) / 7
  - When the start or stop date is missing, then the exposure will be treated as missing. Interruptions, compliance, and dose changes are not taken into account for duration of exposure.
- Number of Doses of GX-188E (times) = Count total numbers from "Exposure GX-188E Vaccination" CRF page with response of "Yes" to the question "Was GX-188E administered at this visit?"
- Duration of exposure to Pembrolizumab (weeks)= (Last dose date of Pembrolizumab First dose date of Pembrolizumab +1) / 7
  - When the start or stop date is missing, then the exposure will be treated as missing. Interruptions, compliance, and dose changes are not taken into account for duration of exposure.
- Number of Doses of Pembrolizumab (times) = Count total numbers from "Exposure Pembrolizumab" CRF page with response of "Yes" to the question "Was Pembrolizumab administered at this visit? "

Document: \\ieedc-vnac01\Biosdata\Genexine\GX-188E\GYA02599\Biostatistics\Documentation\SAP

Author: [name] Version Number: 1.1

Version Date: 05Sep2022

Template No: CS\_TP\_BS016 Revision 6 Reference: CS\_WI\_BS005

Analysis Plan Page 26 of 48

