#### 4.2. INTERIM ANALYSIS

An interim analysis will be performed with safety and efficacy data in case of at least 22 patients in efficacy evaluation population, after obtaining week 10 tumor assessment results (by investigator/BICR).

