## 4.3. FINAL ANALYSIS

The final analysis will be performed to report a primary CSR based on a data cut off after all 60 patients in the planned efficacy evaluation population have completed tumor assessment within 24 weeks by the investigator per RECIST v1.1

Since patient will be treated until they met one of the discontinuation criteria, some patients may still be ongoing at the time of final analysis. Therefore, a long-term follow-up study can be performed after final analysis with all available data (no cut-off date applied).

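### Pembrolizumab exposure duration is set to missing for patients still on treatment at the cut-off, so the summary covers only those who have stopped and is expected to run short

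*SAP*

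**What the plan says.** SAP 13 (Study Medication Exposure) summarises exposure for the safety population. It reads the first-dose date from the per-visit Exposure forms. For the last dose it uses a different source: "The date of last study medication will be taken from the" date-of-last-administration field on the End of Treatment page, for GX-188E and for pembrolizumab.

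SAP 13.1 defines duration for each drug as (last dose date − first dose date + 1)/7 weeks and adds, once per drug, "When the start or stop date is missing, then the exposure will be treated as missing". Number of doses is derived differently, by counting the visits at which the Exposure page records an administration.

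SAP 7.3 offers no way round this: "Generally, missing data will not be imputed". Its exceptions are partial death dates and partial dates for adverse events and medications.

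SAP 4.3 sets the final "data cut off after all 60 patients in the planned efficacy evaluation population have completed tumor assessment within 24 weeks" and states that "some patients may still be ongoing at the time of final analysis"; Protocol 24.8 says the same. SAP 4.2 places the interim analysis "after obtaining week 10 tumor assessment results" in at least 22 patients. Pembrolizumab may continue to 35 doses (Protocol 19.1), with the last at Week 103 Day 1 (Protocol 16.11.1).

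**The concern.** Whether duration is missing depends on the quantity being summarised. A patient is left out because her treatment has not ended, and the patients left out tend to be those whose treatment lasts. The table would carry the safety population's label but describe only the patients who had stopped. It would also be inconsistent within itself, because the number of doses would cover everyone and the duration would not.

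Duration of pembrolizumab exposure is a descriptive variable, but it is one that a reader of the study report uses to judge how long patients were observed on drug when adverse events are interpreted. At the interim analysis, as early as the week 10 assessment, the share of patients still on treatment could be larger than at the final one.

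**Working it through.** **1. The plan's own maximum.** Dose 35 of a 3-weekly schedule falls in week 1 + 3 × 34 = 103, which agrees with Protocol 16.11.1. The SAP 13.1 formula gives a longest scheduled duration of (34 × 21 + 1)/7 = 102.1 weeks. The final cut-off need only wait for the 24-week assessments, so a patient can be well short of the end of treatment when the data are cut.

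**2. The rule applied to one ongoing patient.** She has no End of Treatment record for pembrolizumab, so there is no last-dose date (SAP 13). Her duration is therefore missing (SAP 13.1). No imputation rule applies (SAP 7.3), and no text substitutes the cut-off date or the last recorded dose. She is not in the summary.

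**3. Size.** The documents give neither accrual time nor expected time on treatment, so the following inputs are assumptions:

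- time on pembrolizumab exponential with median m = 4, 6 or 8 months, capped at 24 months;
- uniform accrual over A = 18 or 36 months;
- cut-off at a = 24 × 7/30.4375 = 5.52 months after the last first dose.

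With λ = ln 2/m and b = min(a + A, 24), the expected share ongoing is

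(e^(−λa) − e^(−λb)) / (λA).

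For m = 6 and A = 18: λ = 0.1155 and b = 23.52, so the share is (0.5285 − 0.0661)/2.079 = 22.2%. The medians come from simulation under the same assumptions.

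| Median on treatment (months) | Accrual (months) | Ongoing | Median, stopped patients only (SAP rule) | Median, all patients to cut-off | Shortfall |
|---|---|---|---|---|---|
| 4 | 18 | 11.8% | 3.37 | 4.01 | 0.64 |
| 4 | 36 | 5.9% | 3.67 | 4.00 | 0.33 |
| 6 | 18 | 22.2% | 4.27 | 5.85 | 1.58 |
| 6 | 36 | 11.2% | 5.08 | 5.90 | 0.82 |
| 8 | 18 | 31.4% | 4.85 | 7.01 | 2.16 |
| 8 | 36 | 15.9% | 6.31 | 7.39 | 1.08 |

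**4. Sensitivity to the cut-off.** SAP 4.3 places the cut-off after the last assessment without fixing a date. Moving it 6 months later reduces the ongoing share from 6–31% to 2–16%. With a 4-month median, the reported median becomes 3.8–3.9 against 4.0 months.

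**5. Direction.** A wider grid used accrual of 52 to 208 weeks and median treatment of 9 to 104 weeks, and compared means. The ratio of the SAP-rule mean to the mean using the last dose up to the cut-off was 0.59 to 0.99 in 22 of 24 scenarios. It was 1.02 and 1.03 in the other two, both with a 104-week median and accrual of 156 weeks or more. Understatement is the expected direction but not a certain one.

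**The case against.** The strongest reply is that this is one descriptive variable and that the rest of the exposure reporting is sound. That stands. Number of doses is counted from the Exposure pages for all safety patients and, with 3-weekly dosing, tracks pembrolizumab duration closely. Overall compliance uses dose counts, individual exposure data are listed, and follow-up time is summarised separately. No test and no exposure-adjusted rate uses duration.

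Four stronger readings are tempting, and the documents do not support them:

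- **Both drugs lose their ongoing patients.** Planned vaccination ends at Week 19, with an optional dose at Week 46. If the End of Treatment page is completed separately per drug, a patient still on pembrolizumab may already have a GX-188E stop date. The documents do not say how the page is completed.
- **The longest-treated patients are the ones removed.** Patients who complete 35 doses have ended treatment and are kept, while ongoing patients include recent entrants with only about 24 weeks.
- **Safety results are distorted.** Adverse events are summarised as numbers and percentages of the safety population, which does not depend on duration.
- **Patients will certainly be ongoing, and the bias is certain.** SAP 4.3 says only that they may be, and step 5 shows that the direction can reverse.

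It can also be said that the table shells accompanying the SAP may contain a convention for ongoing patients. They are not available here, and a convention in a shell would contradict the written derivation. A programmer who quietly used the last Exposure-page date would likewise be departing from the SAP.

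**Conclusion.** The point holds for pembrolizumab duration. Followed as written, SAP 13 and 13.1 restrict that summary to patients who have stopped, at both the interim and the final analysis, although it is labelled as covering the safety population. This is a rule that produces a selective summary, and not merely a missing detail.

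The expected effect is a duration that is too short. Under the assumptions in step 3, 6% to 31% of patients are ongoing and the reported median is about 0.3 to 2.2 months low. A later cut-off makes it smaller, and nothing in the documents settles the true figure. GX-188E duration is affected only if the End of Treatment page is not completed separately per drug. Dose counts, compliance, adverse event incidences and the primary endpoint are untouched. The correction is worth making before the analyses are run, but it does not bear on the trial's efficacy conclusion.

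**What to change.** Amend SAP 13 and 13.1, stating the rule separately for GX-188E and pembrolizumab:

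- When there is no End of Treatment date because treatment is ongoing at the data cut-off, take as last dose date the latest administration date on that drug's Exposure page on or before the cut-off.
- Do not set duration to missing for these patients. Keep the missing rule for dates that are truly unknown.
- Report the number of patients ongoing at the cut-off beside the duration summary.
- Apply the same rule at the interim analysis.

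The End of Treatment date may remain the source for patients who have stopped. The fallback does not conflict with SAP 7.3, because it uses a recorded dose date and imputes nothing.

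The cost is a few sentences in the SAP and a small program change. SAP 13 already reads the first-dose date from the Exposure forms and lists their contents, so no new data should be needed.
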